### PROTOCOL TITLE

The Feasibility & Effectiveness of Virtual Reality in Reducing Pain for Older Adults with Knee Osteoarthritis

### FUNDING

- None

### VERSION DATE

06 April, 2022

### SPECIFIC AIMS

1. The purpose of this project is to evaluate the feasibility and effectiveness of VR as a treatment option for older adults with chronic osteoarthritic knee pain.
2. Aim 1: Implement a pilot study and collect data on the feasibility of VR and its effects on pain for older adults with chronic osteoarthritic knee pain.
3. Aim 2: Analyze the feasibility of VR for this population, including looking at simulation sickness factors and drop out reasons/rates, and its impact on chronic pain immediately prior to and immediately post intervention, as well as a few days post intervention.
4. Sub-study Aim 1: The aim of this sub-study is to compare the effectiveness of a virtual reality meditation session and a non-immersive meditation session for improving pain, affect, and physiological vital stats in adults with fibromyalgia.
5. Sub-study Aim 2: We hypothesize that the VR meditation session will facilitate greater improvements in pain, affect, and physiological vital stats as compared to the non-immersive meditation intervention.

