### BACKGROUND AND SIGNIFICANCE

Thirty percent of older adults in the United States report experiencing chronic pain, with 41% of this subset of the population experiencing chronic joint pain (NIH Pain Consortium, n.d.). Knee osteoarthritis (OA) affects 37% of individuals aged 60 years or older who participated in the National Health and Nutrition Examination (Sharma, 2021). This condition typically involves pain, stiffness, reduced joint motion and muscle weakness, and chronic pain that can have profound effects on physical function, psychological parameters, and overall quality of life. Past studies at the PMC have looked at the physiological mechanisms involved with chronic knee OA and the older adult population, the site has had limited funding to research nonpharmacological treatments such as virtual reality. Virtual reality has been shown to be feasible for a variety of populations, including young people with autism experiencing specific phobia, pediatric

burn patients, and young adults (Maskey et al., 2019; Hoffman et al., 2014, Sakhare et al., 2019). However, there is limited evidence on the feasibility of VR for treating pain for the older adult population. This study aims to study the effectiveness of VR for chronic pain for older adults and is necessary to determine best methods to feasibly integrate VR into clinical practice.

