## RESEARCH DESIGN AND METHODS

We will recruit 25 older adults with knee osteoarthritis from Brigham and Women's Hospital (BWH) to obtain 20 subjects with complete data collection. The sub-study will enroll 25 adults with fibromyalgia from BWH.

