#### **EXPECTED BENEFITS**

Participants have the potential to experience reduced pain symptoms during and after the VR experience. This result is very probable. Previous experiences suggest that the magnitude of this effect is, on average, large, and that the duration will be during the Virtual Reality experience and possibly up to a few hours or days afterwards.

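### The knee osteoarthritis study says it evaluates effectiveness, but a single-arm pilot of VR-delivered meditation can support only the feasibility aims and a description of pain change

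*Protocol*

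**What the plan says.** The title names both feasibility and effectiveness. The first item under Specific Aims says the project will "evaluate the feasibility and effectiveness of VR as a treatment option" for this cohort. Background and Significance repeats it: "This study aims to study the effectiveness of VR for chronic pain for older adults".

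The aims below that are more modest. Aim 1 is to "Implement a pilot study and collect data on the feasibility of VR and its effects on pain". Aim 2 covers feasibility, simulation sickness, drop-out and "its impact on chronic pain immediately prior to and immediately post intervention, as well as a few days post intervention".

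Research Design and Methods fixes the size: "We will recruit 25 older adults with knee osteoarthritis from Brigham and Women's Hospital (BWH) to obtain 20 subjects with complete data collection". Under Study Design every knee osteoarthritis participant follows the same path: baseline surveys, one 10-20 minute guided meditation through the headset, post-session surveys, and a remote survey within a few days. Pain, affect and global impression of change are all self-reported. No control condition, crossover or randomisation is described for this cohort. The non-immersive meditation session belongs to the fibromyalgia sub-study.

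Expected Benefits says of reduced pain: "This result is very probable". It adds that the effect is large on average, and gives previous experiences, without a reference, as the basis.

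**The concern.** Effectiveness is a causal claim: pain is lower because of VR than it would have been without it. The main study observes no one without VR, so its only contrast is each person against themselves earlier. That contrast contains everything else that happened around the session. The most direct rival explanation is the guided meditation, because it is delivered through the headset and is never given without it in this cohort. Rest (participants are generally seated), staff attention, expectancy in people who know what they received, and ordinary fluctuation in chronic pain are also mixed in.

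What is at stake is the conclusion the trial is allowed to draw. If the purpose statement stands, an observed fall in pain invites a conclusion that the data cannot support, and no analysis can supply the missing comparison afterwards.

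**Working it through.** **1. Claim and design compared.**

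| Element | Knee osteoarthritis study | Fibromyalgia sub-study |
|---|---|---|
| Stated purpose | Feasibility and effectiveness | Comparative effectiveness |
| Conditions | VR-delivered meditation only | VR-delivered and non-immersive meditation |
| Contrast available | Before versus after | Between conditions, as well as before versus after |
| Can VR be separated from meditation? | No | The comparator is there for that purpose |

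The feasibility items in Aim 2 (sickness symptoms, drop-out) need no comparator. The effectiveness item does.

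**2. The plan's own figure.** Recruiting 25 to obtain 20 complete implies a loss of 1 − 20/25 = 20%, and 20/(1 − 0.20) = 25. The two numbers agree. The protocol gives no SD, effect size, alpha or power for this cohort, so the 20 itself cannot be derived.

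**3. Illustration of how often a non-specific change would look like an effect.** Every input here except the sample size is an assumption:

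- Pain SD σ = 1.5 to 3 points; before-after correlation r = 0.4 to 0.8.
- A two-sided paired t-test at 5%. The protocol names no test for this cohort.
- n = 20 to 25 (Research Design and Methods).
- True VR effect zero; non-specific mean fall δ = 0.5 or 1.0 point.

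Formulas: SD of change = σ√(2(1 − r)); noncentrality = δ√n / SD of change; the rejection rate comes from the noncentral t with n − 1 degrees of freedom.

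- Widest spread: 3 × √(2 × 0.6) = 3.29.
- Narrowest spread: 1.5 × √(2 × 0.2) = 0.95.
- A middle case, σ = 2 and r = 0.7: 2 × √(2 × 0.3) = 1.55.

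| SD of change | n | δ = 0.5 | δ = 1.0 |
|---|---|---|---|
| 3.29 | 20 | 9.9% | 25.3% |
| 1.55 | 20 | 27.8% | 78.2% |
| 1.55 | 25 | 34.1% | 87.2% |
| 0.95 | 25 | 71.5% | 99.9% |

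The ranges are therefore about 10% to 72% for a half-point fall and about 25% to 100% for a one-point fall. With n = 20, any observed mean fall of at least 2.093/√20 = 0.47 SD of change is significant, whatever caused it. A comparison with a concurrent group sharing the same non-specific fall would reject at the nominal 5%.

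**4. Limit of the illustration.** It presumes the same pain scale before and immediately after the session. Baseline Surveys lists the Brief Pain Inventory-Short Form and no numeric rating scale, while Post-Intervention Surveys lists two numeric rating scales. The text does not establish a paired analysis of a single scale, so the figures show only the order of the problem.

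**The case against.** The best defence is that this is declared a pilot, that one arm is the normal choice for feasibility, and that the protocol states no hypothesis, test or success criterion for the knee osteoarthritis cohort. All of that stands. It is why nothing here asks for another arm, and why the defect is confined to what the study says it will conclude.

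Four stronger readings are tempting, and the protocol does not support them.

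- A reader might infer that any fall in pain will be reported as a VR effect. No reporting rule says so; the only stated hypothesis belongs to the sub-study, and a statistical analysis plan may exist that is not shown.
- A reader might see the benefit statement as contradicting the Background. It does not: the Background says "there is limited evidence on the feasibility of VR for treating pain" in older adults, which concerns feasibility, whereas Expected Benefits concerns the size of relief and is not limited to older adults. It also opens by speaking only of potential.
- A reader might infer that the optimistic benefit wording will bias participants' ratings. Nothing shows that it is told to them, and the consent pages are not available.
- A reader might take the rejection rates as false-positive rates for this trial. They depend on an assumed test and assumed inputs.

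What remains is that effectiveness is stated in the title, the purpose statement and the Background, and that the design of this cohort lacks the comparison that the word requires. An analysis plan could limit the claim but could not make it estimable.

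**Conclusion.** The point holds as a mismatch between stated purpose and design. The knee osteoarthritis study can deliver its feasibility aims and describe within-person change in pain after a VR-delivered meditation; it cannot show that VR is effective. This rests on the protocol's description of the cohort and on no numerical assumption. The size is illustrative only: about 10% to 72% (0.5-point fall) or 25% to 100% (1.0-point fall) of studies with no VR effect would show a significant change, under the assumed inputs.

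The benefit statement is a secondary matter. It is optimistic and unreferenced, but it does not cause the confounding. The point does not extend to the sub-study, which has a comparator; whether that comparison is otherwise well specified is not judged here.

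**What to change.** For the main study, replace 'effectiveness' in the title, the purpose statement under Specific Aims and the Background with 'feasibility and preliminary within-person change in pain after a VR-delivered meditation'. Add one sentence saying that the pre/post change will be reported as an estimate with a 95% CI and will not be attributed to VR.

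In Expected Benefits, reword the statements on probability and size so that benefit is described as possible but not established.

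The cost is a protocol wording amendment, with no new arm, visit or participant. The downside is a more modest stated conclusion.

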#### Baseline Surveys

At the in-person visit the participant will complete the following baseline questionnaires collected via paper and pencil or REDCap, demographics, brief medical history, past experience with VR, the Pain Catastrophizing Scale (PCS), Survey of Pain Attitudes (SOPA), the Positive and Negative Affect Scale (PANAS), the PROMIS Emotional Distress Short Form, and the Brief Pain Inventory-Short Form. Answering the surveys will take 10-20 minutes.

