#### Post-Intervention Surveys

After the intervention, the subject will spend about 10-20-minutes filling out post-intervention questionnaires via paper or electronically via REDCap. The questionnaires include, the subject's VR experience, the User Engagement Scale, the Igroup Presence Questionnaire, the Simulator Sickness Symptoms, the Meditation Experience Questionnaire, 2 Numeric Rating Scale for pain, the PANAS, and the Patient Global Impression of Change (PGIC). Then, we will ask a short set of open-ended questions related to overall experience with the VR and meditation, feedback about the session, and willingness to utilize this intervention again. We will audio tape the responses.

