#### Follow-Up Questionnaires

Prior to ending the session we will determine if the subject prefers to complete the follow-up questions by phone or by electronic questionnaire. Within a few days after the intervention, we will contact the participant via their preferred method to complete the surveys at home. These surveys include, the BPI-SF, the PGIC, the PANAS, the PROMIS Emotional Distress Short Forms for anxiety, depression and anger, the PCS. If we have not heard from subject within 24 hours after sending the follow-up surveys, we will contact participants to remind or assist them with completing follow-up questionnaires. These surveys will take about 10-20 minutes to complete.

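### The knee osteoarthritis study does not say which pain change decides effectiveness, and its immediate before/after change has no listed pain scale on both sides

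*Protocol*

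**What the plan says.** The Protocol's Specific Aims state the purpose of the main study as to "evaluate the feasibility and effectiveness of VR as a treatment option for older adults with chronic osteoarthritic knee pain". Aim 2 then asks about "its impact on chronic pain immediately prior to and immediately post intervention, as well as a few days post intervention". Neither later time is ranked above the other, and no pain scale is named as the one that decides.

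The measurements sit in three places under Study Design:

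- **Baseline Surveys**, at the visit before the session. The list ends with "the PROMIS Emotional Distress Short Form, and the Brief Pain Inventory-Short Form". It contains no NRS for pain.
- **Post-Intervention Surveys**, straight after the session. The list includes "2 Numeric Rating Scale for pain, the PANAS, and the Patient Global Impression of Change (PGIC". It contains no BPI-SF. The text does not say what each of the two NRS items rates.
- **Follow-Up Questionnaires**, a few days later: "These surveys include, the BPI-SF, the PGIC, the PANAS, the PROMIS Emotional Distress Short Forms for anxiety, depression and anger, the PCS". There is no NRS.

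Expected Benefits says of the relief that "the duration will be during the Virtual Reality experience and possibly up to a few hours or days afterwards". The main study describes no comparator; the non-immersive session belongs to the fibromyalgia sub-study.

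**The concern.** The two later times answer different questions. Pain straight after one session shows short-lived relief around that session. Pain a few days later bears on whether the chronic condition has changed. Expected Benefits is confident about the first and only tentative about the second, so the Protocol itself foresees that they may disagree. If they do, the aims as written support either conclusion about VR as a treatment option, and the choice could be made with the results in view.

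The missing decision also hides a practical gap. Anyone naming the immediate pain change as the deciding contrast would at once look for the same pain scale before and after the session. The listed batteries do not supply one. If the study is run exactly as listed, one of Aim 2's two pain comparisons cannot be formed as a within-scale change in pain intensity, and this cannot be repaired once participants have been seen.

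**Working it through.** **Step 1. The Protocol's own figure.** Research Design and Methods recruits 25 to obtain 20 with complete data. The implied loss is 1 − 20/25 = 20%, and 20/(1 − 0.20) = 25, so the figure reproduces. The Protocol gives no alpha, power, effect size or SD, so there is no power calculation to check. I take n = 20 forward.

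**Step 2. The main-study pain measures side by side.**

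| Measure | Before session | Straight after | A few days later |
|---|---|---|---|
| Pain NRS | not listed | two items | not listed |
| BPI-SF | listed | not listed | listed |
| PGIC | not listed | listed | listed |

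- Before to straight after: no pain-intensity scale appears in both columns.
- Before to a few days later: the BPI-SF appears in both columns, so a within-scale change can be computed.
- The PGIC spans both later times. It asks the participant for a global judgement of change, so it is neither a pain-intensity score nor a before/after difference.

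For contrast, the sub-study lists a pain NRS both in Pre-intervention Tasks and after the session.

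**Step 3. The price of leaving the choice open.** These inputs are assumptions, because the Protocol states none of them: two-sided alpha 0.05, paired t-tests, no true change, and two pain contrasts, one at each later time. The calculation also assumes that a matched pre-session NRS is in fact collected; otherwise the immediate contrast does not exist.

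For independent contrasts:

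- At least one significant result in either direction: 1 − 0.95² = 0.0975.
- At least one significant result in the benefit direction: 1 − 0.975² = 0.0494, against 0.025 for one named contrast.

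For correlated contrasts, simulation of 100,000 null studies with n = 20 gives:

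| Correlation | Either direction | Benefit direction |
|---|---|---|
| 0 | 9.8% | 5.0% |
| 0.3 | 9.3% | 4.7% |
| 0.5 | 9.1% | 4.6% |
| 0.7 | 8.4% | 4.2% |
| 0.9 | 7.1% | 3.5% |

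With one contrast named in advance, the rates are 5% and 2.5%. The open choice therefore multiplies the error by about 1.4 (7.1/5) to 2 (9.8/5).

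**The case against.** The strongest reply is that this is a small pilot. Feasibility comes first in both aims, the main study states no hypothesis (only the sub-study does), and Aim 2 commits to analysing both times. Tests, multiplicity and outcome labels may sit in an SAP that is not at hand. Much of this stands. It limits how serious the point is, and it means that selection after the fact is a possibility left open, not something the Protocol plans. It does not remove the point. The Protocol chose an effectiveness purpose, which pain question answers it belongs with the aims, and an SAP cannot supply a baseline rating that was never taken.

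Some stronger readings are tempting, but the documents do not support them:

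- A reader might infer that the two later times share no instrument. They share the PGIC, and the BPI-SF is at baseline and follow-up. Only the pain-intensity measures differ between the two later times.
- A reader might infer that a fall at either time on any scale would count as success. The Protocol states no success rule of any kind.
- A reader might count every scale in the two batteries and quote a much larger error rate. Aim 2's effectiveness wording concerns pain. The PANAS, PROMIS and PCS do not measure pain intensity, and counting both NRS items as change scores presumes a baseline that is not listed.
- A reader might conclude that no pre-session NRS exists. The Protocol does not list one, but it also does not say what the two post-session items rate; one could be a recalled pre-session rating. The text needs clarifying.

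**Conclusion.** The point holds in this form: the main study has an effectiveness purpose, Aim 2 leaves immediate and few-days pain unranked, and as listed the immediate change in pain intensity has no same scale on both sides. The BPI-SF from baseline to follow-up is the only clearly computable within-scale pain change.

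The false-positive cost is modest: about 7% to 10% two-sided for two pain contrasts, or about 5% in the benefit direction if they are independent (3.5% at correlation 0.9), against 2.5% for one. These rates rest on the assumed alpha, test, correlation and number of contrasts. The unranked aims and the unmatched scales rest on none of those assumptions; they come from the text alone. The sample size is not at fault. The point should be fixed before data are collected, in proportion to a pilot.

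**What to change.** 1. In Baseline Surveys, list the same pain NRS item immediately before the session as is used after it, or state in Post-Intervention Surveys what each of the two NRS items rates.
2. In Aim 2, name one deciding pain contrast for the main study. Use the matched NRS change around the session if the question is short-term relief, or the BPI-SF severity change from baseline to follow-up if the claim is about chronic pain.
3. Make the other contrast the key secondary. Label the remaining measures exploratory and report them as estimates with 95% confidence intervals.
4. State that an immediate fall alone, with no comparator, will be described as short-term change around a session and not as an effect on chronic pain.

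The cost is one or two extra rating items and a few sentences, with no extra participants or visits. The downside is that a favourable result on another scale or at the other time can no longer be presented as the main pain result.

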### BACKGROUND AND SIGNIFICANCE

Thirty percent of older adults in the United States report experiencing chronic pain, with 41% of this subset of the population experiencing chronic joint pain (NIH Pain Consortium, n.d.). Knee osteoarthritis (OA) affects 37% of individuals aged 60 years or older who participated in the National Health and Nutrition Examination (Sharma, 2021). This condition typically involves pain, stiffness, reduced joint motion and muscle weakness, and chronic pain that can have profound effects on physical function, psychological parameters, and overall quality of life. Past studies at the PMC have looked at the physiological mechanisms involved with chronic knee OA and the older adult population, the site has had limited funding to research nonpharmacological treatments such as virtual reality. Virtual reality has been shown to be feasible for a variety of populations, including young people with autism experiencing specific phobia, pediatric

burn patients, and young adults (Maskey et al., 2019; Hoffman et al., 2014, Sakhare et al., 2019). However, there is limited evidence on the feasibility of VR for treating pain for the older adult population. This study aims to study the effectiveness of VR for chronic pain for older adults and is necessary to determine best methods to feasibly integrate VR into clinical practice.

#### Sub-study:

Fibromyalgia (FM) is a debilitating rheumatological syndrome which affects millions of adults in the United States. The condition presents with widespread chronic muscular pain and reduced pain thresholds (CDC, 2020). Additional symptoms that often accompany FM include fatigue, insomnia, and negative affect. As with knee OA, the chronic pain that is caused by FM can have significant effects on physical function, psychological parameters, and overall quality of life. Just as VR distraction may be a useful tool for clients experiencing chronic knee OA, the same principles apply for pain management for those with FM. Previous research has demonstrated that affect was improved for clients with FM who participated in a 10-minute VR mindfulness session (Botella, et al, 2013). Such findings highlight the potential benefits of VR and mindfulness meditation for clients with FM. There is a great deal that remains unknown about the effectiveness of these pain management techniques. This pilot study will examine and compare the effectiveness of combining VR and meditation for improving symptoms of FM in adults.

## RESEARCH DESIGN AND METHODS

We will recruit 25 older adults with knee osteoarthritis from Brigham and Women's Hospital (BWH) to obtain 20 subjects with complete data collection. The sub-study will enroll 25 adults with fibromyalgia from BWH.

